6.15.8. Follow-up of Adverse Events Present at Last Scheduled Study Visit

Adverse events present at the last study day (Week 26/Exit) that require follow-up or a repeat laboratory test will be followed up initially for 30 days according to the site's standard practice for AE follow-up. AEs that have not resolved or stabilized at 30 days after the last patient's last study dose, will be reviewed with the sponsor on an individual basis to determine whether the database will be locked and subsequently updated once the events of ongoing AEs are resolved or whether database lock will be held.

6.16. Drug-Induced Liver Injury (DILI) Surveillance

In July 2009, the FDA released a Guidance for Industry entitled "Drug-Induced Liver Injury: Premarketing Clinical Evaluation," which reviews the importance of DILI surveillance in drug development. DILI has been the most frequent single cause of safety-related drug marketing withdrawals for the past 50 years, and hepatotoxicity discovered after approval for marketing has limited the use of many drugs. Furthermore, the guidance addresses how laboratory measurements that signal the potential for DILI can be obtained and evaluated during drug development.

Given the fact that all subjects enrolled in this study have pre-existing liver disease (i.e., PBC) and baseline elevations in laboratory tests of liver health (ALP, ALT and/or AST), DILI

surveillance is of critical importance to patient safety. Therefore, in collaboration with the FDA and after careful consideration of the principles outlined in the DILI guidance, the sponsor has established procedures to ensure early detection of possible DILI and study drug discontinuation in the context of suspected DILI.

6.16.1. Close Observation for Possible DILI

It is critical to initiate close observation immediately upon detection and confirmation of early signals of possible DILI, and not to wait until the next scheduled visit or monitoring interval. Close observation is mandatory for any study patient who meets one or more of the following “possible DILI” laboratory criteria:

- ALT or AST that is $<ULN$ at baseline, followed by ALT or AST increase to $>3 \times ULN$
- ALT or AST that is $>ULN$ at baseline, followed by ALT or AST increase to $>2 \times$ baseline
- ALP $>2 \times$ baseline
- Total bilirubin $>1.5 \times ULN$

Close observation includes:

- Repeating liver enzyme and serum bilirubin tests within 48-72 hours. Then, repeating liver enzyme and serum bilirubin tests two or three times weekly. Frequency of retesting can decrease to once a week or less if abnormalities resolve, abnormalities stabilize, or the study drug has been discontinued and the subject is asymptomatic.
- Obtaining a more detailed history of symptoms and prior or concurrent diseases.
- Obtaining a history of concomitant drug use (including nonprescription medications and herbal and dietary supplement preparations), alcohol use, recreational drug use, and special diets.
- Ruling out acute viral hepatitis types A, B, C, D, and E; autoimmune or alcoholic hepatitis; nonalcoholic steatohepatitis; hypoxic/ischemic hepatopathy; and biliary tract disease.
- Obtaining a history of exposure to environmental chemical agents.
- Obtaining additional tests to evaluate liver function, as appropriate (e.g., INR, direct bilirubin).
- Considering consultations, imaging studies, and/or therapeutic interventions, as required.

6.16.2. Study Drug Discontinuation for Suspected DILI

Should any patient who meets “possible DILI” laboratory criteria have persistence or worsening of lab data (i.e., ALT, AST, ALP, and/or total bilirubin) after one week of close observation, study drug must be discontinued. In addition, immediate study drug discontinuation is mandatory for any study patient who meets one or more of the following “suspected DILI” clinical criteria:

- ALT or AST $<2 \times$ ULN at baseline, followed by ALT or AST increase to $>5 \times$ baseline
- ALT or AST $\geq 2 \times$ ULN but $<5 \times$ ULN at baseline, followed by ALT or AST increase to $>3 \times$ baseline
- ALT or AST increase to $>2 \times$ baseline AND concomitant total bilirubin increase to $>2 \times$ baseline
- ALT or AST increase to $>2 \times$ baseline AND concomitant INR increase >0.2
- Clinical signs and symptoms of liver inflammation, including but not limited to fatigue, nausea, vomiting, right upper quadrant pain or tenderness, fever, rash, jaundice, icterus, and/or eosinophilia ($>5\%$)

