4.1.1. Inclusion Criteria

1. Males or females aged 18 to 80 years (inclusive) at the time of screening, with confirmed PBC diagnosis based upon at least 2 of 3 criteria:
 - AMA titer >1:40 on immunofluorescence or M2 positive by enzyme-linked immunosorbent assay (ELISA) or positive PBC-specific antinuclear antibodies (anti-GP210 and/or anti-SP100)
 - ALP >1.5 × ULN for at least 6 months
 - Liver biopsy findings consistent with PBC
2. Use of UDCA for at least 6 months prior to screening (stable dose for at least 3 months immediately prior to screening)

- 
4. Patients must have the following laboratory parameters at screening
 - ALP >1.5 × ULN but <10 × ULN (at all screening visits)
 - ALT and AST <5 × ULN (at all screening visits)
 - Total bilirubin <ULN (at all screening visits)
- 

[figure not shown]
8. AST, ALT, ALP, and total bilirubin must have 2 values at least 4 weeks apart that are within 20% of each other.

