6.9.1. List of Laboratory Parameters

Laboratory tests will include the following:

Serum Chemistry

Albumin (ALB)
Alkaline phosphatase (ALP)
Alanine aminotransferase (ALT; SGPT)
Amylase
Aspartate aminotransferase (AST; SGOT)
Bicarbonate
Blood urea nitrogen (BUN)
Calcium (Ca)
Chloride (Cl)
Creatinine
Creatine kinase and MB subtype (if elevated) (% and total MB)*
Gamma-glutamyl transferase (GGT)
Glucose
Lactate dehydrogenase (LDH)
Lipase
Magnesium
Phosphate
Potassium (K)
Sodium (Na)
Total bilirubin
Direct bilirubin
Total protein

Serum Chemistry Lipid Panel

High-density-lipoprotein (HDL)
Low-density-lipoprotein (LDL)
Total cholesterol (TC)
Triglycerides (TG)

Hematology

Hematocrit (Hct)
Hemoglobin (Hb)
Lymphocyte subsets (CD4, CD8 and NK cells)
Mean corpuscular hemoglobin (MCH)
Mean corpuscular volume (MCV)
Platelet count
Red blood cell count (RBC)
White blood cell count (WBC) with differential (% and absolute counts)

Coagulation

Prothrombin time (PT)
Activated partial thromboplastin time (PTT)
International Normalized Ratio (INR)

Additional tests

[REDACTED]
Urine dipstick test
Follicle stimulating hormone (FSH)

[REDACTED]
AMA
[REDACTED]

Additional tests at screening

[REDACTED]
HBsAg
Anti-HCV
[REDACTED]
QuantiFERON
Thyroid-stimulating hormone (TSH)
Triiodothyronine (free T3)
Thyroxine (free T4)

* alternatively, this can be done by troponin test (T and or I)

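### The mandatory ALT/AST-plus-INR stop cannot be routinely assessed at several on-treatment visits, which matters mainly for patients with ALT/AST below ULN at baseline

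*Combined protocol and SAP*

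**What the plan says.** Section 6.16.2 lists criteria that each force immediate discontinuation. One is ALT or AST above 2 x "baseline AND concomitant INR increase >0.2". A parallel criterion pairs the same enzyme rise with bilirubin: ALT or AST above 2 x "baseline AND concomitant total bilirubin increase to" more than 2 x its own baseline. Separate limbs stop drug on ALT/AST alone (above 5 x baseline if baseline is below 2 x ULN; above 3 x baseline if it is 2 to below 5 x ULN) and on symptoms. The same section also stops drug if a patient under close observation has results that persist or worsen after one week.

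Section 6.16.1 starts close observation on ALT/AST at more than 3 x ULN when baseline is below ULN, and at more than 2 x baseline when baseline is above ULN. ALP above 2 x baseline or total bilirubin above 1.5 x ULN also starts it. Liver enzymes and bilirubin must then be repeated. INR is only an example among further tests: "Obtaining additional tests to evaluate liver function, as appropriate (e.g., INR, direct bilirubin".

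Section 6.9.1 puts INR under Coagulation and total bilirubin under Serum Chemistry. In section 7.2, coagulation is listed at 7.2.1, 7.2.4, 7.2.7 and, within 7.2.6, at Week 16 only. Inclusion criterion 4 gives the transaminases an upper limit only: "ALT and AST <5 × ULN (at all screening visits".

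**The concern.** A stop rule works only if its inputs are measured. Bilirubin comes with every chemistry draw, so the bilirubin limb can be assessed whenever ALT and AST are. INR does not, and no visible text requires one once the enzyme limb is met. A patient could therefore meet a mandatory stop criterion and stay on drug because nobody had to measure the second component. Safety is the primary objective, section 6.16 treats liver surveillance as critical in these patients, and the decision to escalate to 2 mg falls at Week 12, after the longest stretch without a scheduled INR.

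**Working it through.** The plan gives no figure to reproduce. The check has three parts.

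**1. Visits with chemistry but no coagulation (section 7.2 lists)**

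| List | Chemistry visits | With coagulation |
|---|---|---|
| 7.2.1 (first dose) | 1 | 1 |
| 7.2.2 | 1 | 0 |
| 7.2.3 | at least 2 | 0 |
| 7.2.4 (Week 12) | 1 | 1 |
| 7.2.5 (escalated only) | 1 | 0 |
| 7.2.6 | at least 2 | 1 (Week 16) |
| 7.2.7 (Week 24) | 1 | 1 |

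7.2.3 covers more than one visit because its lipid panel is marked for Week 4 only. 7.2.6 does so because its coagulation is marked for Week 16 only. Visit headings are blacked out, so the counts are minimums.

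After the first dosing visit:
- Escalated: 1 + 2 + 1 + 1 + 2 + 1 = 8 chemistry visits, 3 with coagulation, 5 without.
- Non-escalated: 1 + 2 + 1 + 2 + 1 = 7, 3 with, 4 without.

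Scheduled INRs during treatment fall at first dose and Weeks 12, 16 and 24, leaving gaps of 12, 4 and 8 weeks.

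**2. Baseline ALT or AST below ULN**

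Let b be the baseline in multiples of ULN, b < 1. The INR limb's enzyme threshold is 2b, close observation starts above 3, and the ALT/AST-alone stop applies above 5b. The range with no ALT/AST-based prompt is 2b to min(3, 5b). The baselines below are assumed for illustration.

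| b | 2b | 5b | Range without a prompt (x ULN) | Part above ULN |
|---|---|---|---|---|
| 0.3 | 0.6 | 1.5 | 0.6–1.5 | 1.0–1.5 |
| 0.4 | 0.8 | 2.0 | 0.8–2.0 | 1.0–2.0 |
| 0.5 | 1.0 | 2.5 | 1.0–2.5 | all |
| 0.6 | 1.2 | 3.0 | 1.2–3.0 | all |
| 0.8 | 1.6 | 4.0 | 1.6–3.0 | all |
| 0.95 | 1.9 | 4.75 | 1.9–3.0 | all |

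Normal-range enzyme values fall in the range only if 2b < 1, that is b < 0.5.

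Bilirubin covers part of this. With baseline bilirubin c (x ULN) and the enzyme rise present, no bilirubin rule applies up to min(2c, 1.5): 0.6 for c = 0.3, 1.0 for c = 0.5, and 1.5 for c of 0.75 or more. ALP above 2 x baseline, or symptoms, would also trigger action.

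**3. Baseline above ULN**

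Close observation starts at 2b, the same point as the INR limb's enzyme threshold. The immediate ALT/AST-alone stop comes at 5b for b < 2 and at 3b from 2 up to the limit of 5. For b = 1.5 these are 3.0 and 7.5 x ULN; for b = 3.0 they are 6.0 and 9.0. INR is discretionary between those points, but results that persist or worsen after one week of observation force discontinuation without any INR. While the abnormality persists, the missing INR therefore costs about a week.

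**The case against.** The strongest case against is that other rules do most of the work. For above-ULN baselines this is right: early retesting and the one-week rule cap the delay. A reader might infer from the 3.0–7.5 and 6.0–9.0 x ULN ranges that such patients could climb that far with no stop; the one-week rule rules that reading out. What stands is that the criterion calls for an immediate stop.

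For sub-ULN baselines, 6.16.1 can be read literally so that one enzyme above ULN at baseline brings a doubling of either enzyme into observation. The range without a prompt then exists only when both ALT and AST start below ULN. That narrows the gap but does not close it: criterion 4 admits such patients, and the baseline elevations described in 6.16 can be met by ALP alone.

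Investigators may order an INR at any time, and a careful one would see from 6.16.2 why it is needed. So a reader should not infer that the rule can never be applied; it can, at scheduled coagulation visits or by ad hoc testing. But a mandatory stop should not rest on an optional test, and sub-ULN patients in this range have no ALT/AST-based prompt for one.

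Table 1 governs the schedule and is not visible. Appendix 1 says section 7 was added in Amendment 3.0 to reflect it, and the affected lists have no blacked-out blood item beyond PK timing. However, Amendment 4.0 records a further Table 1 change that cannot be read.

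**Conclusion.** The concern holds, mainly for patients with ALT/AST below ULN at baseline (possibly only with both below). Following the visible text, such a patient can meet the INR stop and remain on drug until the next scheduled INR, up to 12 weeks after first dose if no other rule intervenes. For above-ULN baselines the effect is a delay of about a week.

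The uncovered case needs an ALT/AST rise within the range above and an INR increase above 0.2, with no bilirubin, ALP or symptom rule met. In at most 20 non-cirrhotic patients with bilirubin below ULN at screening, it is probably uncommon. The documents do not say how many patients start with ALT or AST below ULN, so no frequency can be given. The absence of a rule requiring an INR is clear in the text; the visit counts carry medium confidence. It should be fixed because the stop is the sponsor's own and the remedy is cheap.

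**What to change.** Do one of the following:
- (i) require a prompt INR whenever ALT or AST exceeds 2 x baseline, whatever the baseline, extending to it the local testing for remote patients that 6.9 allows for close observation; or
- (ii) add coagulation to every on-treatment chemistry visit (7.2.2, 7.2.3, 7.2.5 and all of 7.2.6).

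In either case, amend 6.16.1 and the matching synopsis text so that an INR is mandatory at the start of close observation and at the first 48–72 hour repeat, then with later repeats while ALT or AST stays above 2 x baseline on drug. Leave all thresholds unchanged.

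The cost is a protocol amendment. Option (i) brings some INRs at enzyme values still in the normal range (only for baselines below 0.5 x ULN), and possible recall visits if central results arrive after the patient has left. Option (ii) adds 4 to 5 tubes at visits that already draw blood. Assuming 2–5 mL per tube, that is 4 x 2 = 8 mL to 5 x 5 = 25 mL, taking the 340 mL estimate in 6.9.5 to 348–365 mL, within the 500 mL limit. The extra INRs during close observation cannot be totalled in advance, because their number depends on how long observation lasts.

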6.17. Concomitant Medications and Procedures

All medications (over the counter [OTC] and prescribed) that are taken by patients and all procedures that are performed during the screening period and during the study must be recorded in the electronic case report form (eCRF) with start date/time and stop date/time, if known.

The following should be taken into account with regard to concomitant procedures:

- Patients may not undergo major elective surgery while enrolled in this study.
- Patients may not donate sperm, or oocytes during the study and for 30 days after the last dose of study drug.

6.17.1. Permitted Medications for the Treatment of PBC

[figure not shown]
UDCA should be at a stable dose for at least 3 months prior to screening and continue at pre-study dosing through the study period.

Medications (such as for pruritus and fatigue) used as adjunctive therapy for PBC in combination with UDCA should be at stable doses within 30 days prior to Day 1. These medications may be adjusted during study treatment but all adjustments must be recorded in the concomitant medications source documents and eCRFs.

[figure not shown]
6.17.2. Excluded Medications

The following medications are excluded prior or during the study:

- Drugs not allowed per the UDCA prescribing information

- Fibrates (including bezafibrate) within 30 days prior to Day 1 and during the study.
- Treatment with OCA within 30 days prior to Day 1 and during the study.
- Immunosuppressive, immunomodulating agents

- 
- Investigational agents, other than etrasimod from 30 days prior to Day 1 and during the study.
- 

6.18. Removal of Patients from the Trial or Study Drug

The study may be terminated early if, in the opinion of the sponsor, investigator, or IEC, an unacceptable risk to the safety and welfare of patients is posed by the continuation of the study in light of review of the key safety data. Evidence of macular edema in patients requires study drug discontinuation.

Patients will be free to withdraw from the study at any time should they so wish. A patient may be withdrawn from the study for any of the following reasons (including but not limited to):

- Clinical investigator may remove a patient if, in his/her opinion, it is in the best interest of the patient (including decisions based on the dose-stopping rules).
- Withdrawal of consent: Any patient may withdraw his/her consent from the study at any time. The investigator should make a reasonable attempt to document the specific reason why consent was withdrawn.
- Deviation/noncompliance with the protocol or study drug.
- An AE.
- Lost to follow up.

6.18.1. Handling of Withdrawals

Although a patient is not obliged to give his/her reason for withdrawing prematurely, the investigator will make a reasonable effort to obtain the reason while fully respecting the patient's rights. If there is a medical reason for withdrawal, the patient will remain under the supervision of the study physician until in satisfactory health. Reasonable efforts will be made to contact a patient who fails to attend any follow-up appointments, in order to ensure that he/she is in satisfactory health.

If a patient is prematurely discontinued from this study, every attempt will be made to follow the Week 24/EOS visit procedures. If consented by the patient, effort will be made to conduct a follow-up visit within 2 weeks of discontinuation ([Table 1](#)), if the patient has received at least 1 dose of the study drug.

6.18.2. Replacements

Patients who terminate early from the study due to reasons other than AEs will be replaced.

6.19. Study and Site Discontinuation

The sponsor has the right to terminate this study at any time. Reasons for terminating the study may include, but are not limited to, the following:

- The incidence or severity of AEs in this or other studies indicates a potential health hazard to patients.
- Patient enrollment is unsatisfactory.

Additionally, if more than three patients develop a CTCAE Grade 3 or higher event in the same category, or if three or more patients meet one of the individual stopping rules, the safety and dose escalation review committee (5.5) will convene to evaluate the findings. Further, dosing will be stopped in randomized patients and no new patients will be randomized until the safety and dose escalation review committee reviews and evaluates the findings.

The sponsor will notify the investigator and IEC if the study is placed on hold, or if the sponsor decides to discontinue the study or development program.

The sponsor has the right to replace a site at any time. Reasons for replacing a site may include, but are not limited to, the following:

- Excessively slow recruitment
- Poor protocol adherence
- Inaccurate or incomplete data recording
- Non-compliance with the ICH guidelines for GCP

7. VISIT PROCEDURES

[figure not shown]
7.1. Screening Period (5 to 8 weeks)

7.1.1. Screening Visit 1

Screening Visit 1 is to occur between Week -8 and Week -5. Subjects who do not fulfill all eligibility criteria will not be enrolled in the study.

Screening Visit 1 procedures for all subjects are as follows:

- Obtain informed consent before performing any study-related procedures, including Screening procedures
- Record medical history and demographics
- Verify inclusion and exclusion criteria for eligibility
- Measure body weight and calculate BMI
- Perform physical exam and neurological exam
- Perform 12-lead ECG
- Measure vital signs
- Record any concomitant medications
- Record any AEs

- Obtain blood samples for:
 - 
 - Chemistry, including ALP
 - Complete blood count and lymphocyte subsets
 - Fasting lipid panel
 - Pregnancy test (female subjects only)

- FSH (female subjects to confirm postmenopausal status only)
- Coagulation
- TSH and free T3 and T4
- Obtain urine sample for
 - Urinalysis
 - Urine drug screen

7.1.2. Screening Visit 2

Screening Visit 2 is to occur at least 4 weeks from Screening Visit 1 to determine whether subjects meet Inclusion Criterion 9 (i.e., AST, ALT, ALP, and total bilirubin must have 2 values 4 weeks apart that are within 20% of each other). Subjects who do not fulfill all eligibility criteria will not be enrolled in the study.

Screening Visit 2 procedures for all subjects are as follows:

- Verify inclusion and exclusion criteria for eligibility
- Record any concomitant medications
- Record any AEs
- Obtain blood samples for:
 - Chemistry (AST, ALT, ALP, and total bilirubin only)

For subjects with AST, ALT, ALP, or total bilirubin values from Screening Visits 1 and 2 that are not within 20% of each other, an unscheduled visit within the screening period may be conducted to repeat these assessments.

7.1.3. [REDACTED]

[REDACTED] procedures for all subjects are as follows:

- [REDACTED]
- [REDACTED]
- Record any concomitant medications
- Record any AEs
- Obtain blood samples for:
 - Chemistry, including ALP
 - Complete blood count and lymphocyte subsets
 - Fasting lipid panel
 - Pregnancy test (female subjects only)
 - Coagulation

- [REDACTED]
- Obtain urine sample for:
 - Urinalysis

7.2. Treatment Period (24 weeks)

7.2.1. [REDACTED]

[REDACTED] procedures for all subjects are as follows:

- Record medical history
- Verify inclusion and exclusion criteria for eligibility
- [REDACTED]
- Perform physical exam and neurological exam
- Perform 12-lead ECG [REDACTED]
- [REDACTED]
- Measure vital signs [REDACTED]
- Record any concomitant medications
- Record any AEs
- [REDACTED]
- Obtain blood samples for:
 - PK at up to [REDACTED]
 - Chemistry, including ALP
 - Complete blood count and lymphocyte subsets
 - Fasting lipid panel
 - [REDACTED]
 - Coagulation
- Obtain urine sample for:
 - Urinalysis
 - Pregnancy test (female subjects only)
- Dispense study drug (1 mg etrasimod) and administer tablet at the clinic

7.2.2. [REDACTED]

[REDACTED] procedures for all subjects are as follows:

- [REDACTED]
- Perform physical exam and neurological exam

- Perform 12-lead ECG [REDACTED]
- Measure vital signs [REDACTED]
- Record any concomitant medications
- Record any AEs
- [REDACTED]
- Obtain blood samples for:
 - PK at up to [REDACTED]
 - Chemistry, including ALP
 - Complete blood count and lymphocyte subsets
- Obtain urine sample for:
 - Urinalysis
- Dispense study drug (1 mg etrasimod) and administer tablet at the clinic

7.2.3. [REDACTED]

[REDACTED] procedures for all subjects are as follows:

- [REDACTED]
- Perform physical exam and neurological exam
- Perform 12-lead ECG [REDACTED]
- Measure vital signs [REDACTED]
- Record any concomitant medications
- Record any AEs
- [REDACTED]
- Obtain blood samples for:
 - Chemistry, including ALP
 - Complete blood count and lymphocyte subsets
 - Fasting lipid panel (Week 4 only)
 - Pregnancy test (female subjects only)
- Obtain urine sample for:
 - Urinalysis
- Dispense study drug (1 mg etrasimod) and administer tablet at the clinic

7.2.4. [REDACTED]

The safety and dose escalation review committee will review the PK and safety data from each PBC patient and will make individualized recommendations on whether a patient will remain at the 1 mg dose or escalate to the 2 mg dose at Week 12 as described in 5.5.

[REDACTED] procedures for all subjects are as follows:

- [REDACTED]
- Perform physical exam and neurological exam
- Record any concomitant medications
- Record any AEs

- Obtain blood samples for:
 - Chemistry, including ALP
 - Complete blood count and lymphocyte subsets
 - Fasting lipid panel
 - Pregnancy test (female subjects only)
 - [REDACTED]
 - Coagulation
- Obtain urine sample for:
 - Urinalysis

[REDACTED] procedures for all subjects who dose escalate are as follows:

- Perform 12-lead ECG [REDACTED]
- [REDACTED]
- Measure vital signs [REDACTED]
- Obtain blood samples for:
 - PK [REDACTED]
- Dispense study drug (2 mg etrasimod) and administer tablet at the clinic

[REDACTED] procedures for all subjects who do not dose escalate are as follows:

- Perform 12-lead ECG [REDACTED]
- Measure vital signs [REDACTED]

- Obtain blood samples for:
 - PK [REDACTED]
- Dispense study drug (1 mg etrasimod) and administer tablet at the clinic

7.2.5. [REDACTED]

This visit will take place only for dose-escalated subjects.

[REDACTED] procedures for all subjects are as follows:

- [REDACTED]
- Perform physical exam and neurological exam
- Perform 12-lead ECG [REDACTED]
- Measure vital signs [REDACTED]
- Record any concomitant medications
- Record any AEs
- [REDACTED]
- Obtain blood samples for:
 - PK at up to [REDACTED]
 - Chemistry, including ALP
 - Complete blood count and lymphocyte subsets
- Obtain urine sample for:
 - Urinalysis
- Dispense study drug (2 mg etrasimod) and administer tablet at the clinic

7.2.6. [REDACTED]

[REDACTED] procedures for all subjects are as follows:

- [REDACTED]
- Perform physical exam and neurological exam
- Perform 12-lead ECG [REDACTED]
- Measure vital signs [REDACTED]
- Record any concomitant medications
- Record any AEs
- [REDACTED]
- Obtain blood samples for:
 - Chemistry, including ALP

- Complete blood count and lymphocyte subsets
- Pregnancy test (female subjects only)
- Coagulation (Week 16 only)
- Obtain urine sample for:
 - Urinalysis

[REDACTED] procedures for all subjects who dose escalate are as follows:

- Dispense study drug (2 mg etrasimod) and administer tablet at the clinic

[REDACTED] procedures for all subjects who do not dose escalate are as follows:

- Dispense study drug (1 mg etrasimod) and administer tablet at the clinic

7.2.7. [REDACTED]

[REDACTED] procedures for all subjects are as follows:

- [REDACTED]
- Measure body weight and calculate BMI
- Perform physical exam and neurological exam
- Perform 12-lead ECG [REDACTED]
- Measure vital signs [REDACTED]
- Record any concomitant medications
- Record any AEs

- [REDACTED]
- [REDACTED]
- [REDACTED]
- [REDACTED]
- [REDACTED]
- [REDACTED]
- [REDACTED]

- Obtain blood samples for:
 - PK at [REDACTED]
 - Chemistry, including ALP
 - Complete blood count and lymphocyte subsets
 - Fasting lipid panel
 - Pregnancy test (female subjects only)
 - [REDACTED]

- Coagulation
- Obtain urine sample for
 - Urinalysis

